8.6.3. Reporting and registration of Adverse Events

At each study visit, adverse events (AE) are registered, starting at intake of first dose of investigational product up to 28 days following the last dose of study drug. All AE that occurs during the study and which are observed by the investigator/study nurse or reported

 Version No:
 2.0 Final

 Date:
 10 March 2023

 EudraCT No:
 2022-003855-32

by the subject will be registered in the eCRF regardless of whether they are related to the investigational product or not. Assessment of causal relationship, severity, and whether the AE is considered to be an SAE or not will be done by the investigator directly in eCRF. At minimum, for each AE/SAE, a description of the event is recorded (diagnosis/symptom if diagnosis is missing), start and stop dates, causal relationship, severity, if the AE is considered to be an SAE or not, measures and outcome.

Reporting of Adverse Events (AE)

All AEs shall be registered in the eCRF within 3 working days.

Reporting of Serious Adverse Events (SAE) to Pfizer

Serious adverse events (SAE) are reported to Pfizer, in a protected email with copy to sponsor, on a designated SAE form within 24 hours from when the information received.

For life-threatening events or death, submit the SAE form immediately.

Follow-up information describing the outcome and handling of the SAE is reported as soon as this information is available and not later than 24 hours from when the information is received. The original should be kept in the Investigator Site File.

In addition, SAEs that occur after completion of the active reporting time period as defined above are reportable to Pfizer if the investigator suspects a causal relationship between the Pfizer product and the SAE.

Reporting of potential cases of Drug-Induced Liver Injury (DILI), Assessed Based on Hy's Law criteria

For investigational (non-authorized) medicinal products that are investigational in the United States (irrespective of being authorized elsewhere), interventional clinical study reports with elevations in aspartate aminotransferase (AST) and/or alanine aminotransferase (ALT) in addition to and/or preceding total bilirubin (TBili) elevations (>2 x ULN) are considered potential DILI- (assessed per Hy's law criteria) cases and should always be considered important medical events, even before all other possible causes of liver injury have been excluded.

The threshold of laboratory abnormalities for a potential DILI case depends on the subject's individual baseline values and underlying conditions. Subjects who present with the following laboratory abnormalities should be evaluated further as potential DILI (Hy's law) cases to definitively determine the etiology of the abnormal laboratory values:

- Subjects with AST/ALT and TBili baseline values within the normal range who subsequently present with AST OR ALT values >3 x ULN AND a TBili value >2 x ULN with no evidence of hemolysis and an alkaline phosphatase value <2 x ULN or not available.
- For subjects with baseline AST OR ALT OR TBili values above the ULN, the following threshold values are used in the definition mentioned above, as needed, depending on which value(s) are above the ULN at baseline.
 - Pre-existing AST or ALT baseline values above the normal range: AST or ALT values >2 times the baseline values AND >3 × ULN; or >8 × ULN (whichever is smaller).

 Version No:
 2.0 Final

 Date:
 10 March 2023

 EudraCT No:
 2022-003855-32

 Pre-existing values of TBili above the normal range: TBili level increased from baseline value by an amount of at least 1 × ULN or if the value reaches >3 × ULN (whichever is smaller).

Rises in AST/ALT and TBili separated by more than a few weeks are assessed individually based on clinical judgment; any case where uncertainty remains as to whether it might represent a potential DILI case will be reviewed with the sponsor. The local Pfizer medical colleague for the ISR/CRC will be informed if such a situation occurs during the study and he/she will inform the Hepatic Injury Council that will provide the necessary support for an appropriate evaluation.

The participant should return to the investigator site and be evaluated as soon as possible, preferably within 48 hours from awareness of the abnormal results. This evaluation should include laboratory tests, detailed history, and physical assessment.

In addition to repeating measurements of AST and ALT and TBili for suspected cases of Hy's law, additional laboratory tests should include:

- Albumin
- CK
- · direct and indirect bilirubin
- GGT
- PT/INR
- total bile acids
- alkaline phosphatase

Consideration should also be given to drawing a separate tube of clotted blood and an anticoagulated tube of blood for further testing, as needed, for further contemporaneous analyses at the time of the recognized initial abnormalities to determine etiology.

A detailed history, including relevant information, such as review of ethanol, acetaminophen/paracetamol (either by itself or as a co-formulated product in prescription or over-the-counter medications), recreational drug, supplement (herbal) use and consumption, family history, sexual history, travel history, history of contact with a jaundiced person, surgery, blood transfusion, history of liver or allergic disease, and potential occupational exposure to chemicals, should be collected. Further testing for acute hepatitis A, B, C, D, and E infection and liver imaging (eg, biliary tract) and collection of serum samples for acetaminophen/paracetamol drug and/or protein adduct levels may be warranted.

All cases demonstrated on repeat testing as meeting the laboratory criteria of AST/ALT and TBili elevation defined above should be considered potential DILI (Hy's law) cases if no other reason for the LFT abnormalities has yet been found. Such potential DILI (Hy's law) cases are to be reported as SAEs, irrespective of availability of all the results of the investigations performed to determine etiology of the LFT abnormalities

Reporting of Suspected Unexpected Serious Adverse Reactions (SUSAR)

The SAEs which are assessed by sponsor as SUSAR are reported via a CIOMS form to the European Medicines Agency (EudraVigilance database) according to the specified time frames.

 Version No:
 2.0 Final

 Date:
 10 March 2023

 EudraCT No:
 2022-003855-32

SUSAR that are fatal or life-threatening are reported as soon as possible and no later than 7 days after the incident has become known to the sponsor. Relevant follow-up information is sent thereafter within an additional 8 days. Other SUSAR are reported as soon as possible and no later than 15 days after they have come to the sponsor's knowledge.

Follow-up of Adverse Events

After the initial AE or SAE report, the investigator is required to proactively follow each participant at subsequent visits/contacts. For each event, the investigator must pursue and obtain adequate information until resolution, stabilization, the event is otherwise explained, or the participant is lost to follow.

In general, follow-up information will include a description of the event in sufficient detail to allow for a complete medical assessment of the case and independent determination of possible causality. Any information relevant to the event, such as concomitant medications and illnesses, must be provided. In the case of a participant death, a summary of available autopsy findings must be submitted as soon as possible to Pfizer Safety.

When new, updated, or corrected information about a previously reported SAE is obtained, a follow-up report should be submitted to Pfizer on a new SAE Report Form that includes the data that is new or revised from the previous report. Follow-up information should never be added to a previously submitted report form. Ensure that any new events included on a follow-up report are marked as serious and a causality assessment is provided for each of them.

8.7. Safety Monitoring Committee

A Safety Monitoring Committee will review unblinded data to ensure the safety of participants throughout the duration of the study, as specified in the SMC Charter.

8.8. Annual Safety Report (Development Safety Update Report, DSUR)

As long as the study is in process in Sweden, the sponsor is obliged to submit an annual safety report to the Swedish Medical Products Agency. It defines for which time period the report applies and a list of all SAE that have occurred as well as possibly SUSAR. A summary assessment of the safety situation for the subjects and a benefit/risk evaluation for the study must also be described.

Note that information to EPM about SUSAR and annual safety reporting are requirements according to LVFS but not EPM.

8.9. Procedures in case of emergencies, overdose or pregnancy

The sponsor and investigator are obliged to immediately take the urgent safety measures necessary to protect the subjects from immediate danger. Examples of such measures are to temporarily suspend the clinical trial or to introduce supplementary monitoring measures. The sponsor shall inform the Swedish Medical Products Agency and EPM as soon as possible about the urgent safety measures taken by the investigator or sponsor.

 Version No:
 2.0 Final

 Date:
 10 March 2023

 EudraCT No:
 2022-003855-32

In case of overdose, i.e., administration of a quantity of the medicinal product per administration of cumulatively that is above the maximum recommended dose according to the product labeling, reporting to Pfizer is done only if associated with an SAE.

If a study subject who participates in a clinical trial for investigational products becomes pregnant, the information is reportable to Pfizer regardless of whether there is an associated SAE. subject must be followed up until the birth has taken place.

A report on Exposure During Pregnancy needs to be completed and sent in within 24 h of the information received, regardless of whether there is an associated SAE in the infant or child.

If the fetus/child has any congenital malformation, this must be reported as a serious adverse event (SAE within 24 h). Further instructions to follow are in the Safety Reporting Reference Manual, version 8, provided by Pfizer.

8.10. Procedures in case of exposure during breastfeeding

Breastfeeding occurs if:

- A female is found to be breastfeeding while receiving or after discontinuing the study drug.
- A female nonparticipant is found to be breastfeeding while being exposed or having been exposed to the trial intervention (i.e., environmental exposure). An example of environmental exposure during breastfeeding is a participant family member or healthcare provider who reports that she is breastfeeding after having been exposed to the trial intervention by ingestion.

Exposure during breastfeeding is reportable to Pfizer regardless of whether there is an associated SAE in the infant or child.

8.11. Procedures in case of Environmental Exposure

Occupational/environmental exposure occurs when a person not enrolled in the study as a participant receives unplanned direct contact with, or exposure to, the Pfizer medicinal product. An occupational/environmental exposure is reportable to Pfizer regardless of whether there is an associated AE.

8.12. Procedures in case of Medication Error

Medication errors may result, for example, from the administration or consumption of the study drug by the wrong participant, or at the wrong time, or at the wrong dosage strength.

Medication errors include:

- Medication errors involving participant exposure to the study drug;
- Potential medication errors or uses outside of what is foreseen in the protocol that do or do not involve the study participant.

Medication errors are reportable to Pfizer only when associated with an SAE.

 Version No:
 2.0 Final

 Date:
 10 March 2023

 EudraCT No:
 2022-003855-32

9. Reference Safety Information

The Investigator Brochure (IB) for Nirmatrelvir is the reference safety information used for the assessment of whether an AE is expected or not. The reference safety information for Ritonavir is found in document "FDA report NDC 31722-597-30 March9 2023.pdf".

10. Statistics

Detailed methodology for statistical analyses of the data collected in this study is outlined here and further detailed in a Statistical Analysis Plan (SAP), which will be maintained by the KI (Institute of Environmental Medicine).

Statistical hypothesis

- The null hypothesis (H0) is that there is no placebo-adjusted difference in EQ-5D-5L between nirmatrelvir/ritonavir and placebo/ritonavir at Day 16.
- The alternative hypothesis (H1) is that there is a placebo-adjusted difference in EQ-5D-5L between nirmatrelvir/ritonavir and placebo/ritonavir at Day16.

Provided the primary endpoint shows positive signal for H1, additional endpoints will be tested including:

• Sustained EQ5D difference at Day 45 and Day 90.

10.1. Estimands

10.1.1. Primary estimand

• For a given endpoint, the primary estimand will be the population average treatment effect on the change from baseline over time of nirmatrelvir/ritonavir compared to placebo/ritonavir. Measurements after discontinuation of study intervention will be censored and treated as missing data. Missing data due to censoring, study withdrawal or other reasons (e.g., laboratory failure) will have data imputed based on a missing at random (MAR) assumption. Participants with inadequate compliance will have their values used as-is in the analysis. The population-based treatment effect will be the difference in the mean change from baseline in nirmatrelvir/ritonavir arm compared to placebo/ritonavir.

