4.2. Description of Objectives, Endpoints and Estimands

The primary, secondary and tertiary/exploratory objectives and endpoints assessed (as described in the schedule of activity) to assess the effect of oral Administration of nirmatrelvir/ritonavir in patients with post-COVID-19 symptoms are summarized in the table below.

Objectives	Endpoints	Estimand
Primary	Primary	Primary
To evaluate the effect of oral administration of nirmatrelvir/ritonavir at Day 16 on quality of life	Change from baseline on the EQ-5D-5L VAS scale at day 16	Estimand 1: This estimand is intended to provide a population-level estimate of the mean treatment effect (nirmatrelvir/ritonavir relative to placebo) on a continuous endpoint over time for all randomized/evaluable participants. The difference of Day 16 on EQ-5D-5L VAS scale between the nirmatrelvir/ritonavir and placebo arms in participants with long COVID estimated with a longitudinal analysis that controls for baseline assessment
Secondary	Secondary	Secondary
To evaluate the effect of oral administration of nirmatrelvir/ritonavir in patients with post-COVID-19 symptoms over time on quality of life	Change from baseline on the EQ-5D-5L VAS scale at day 45 and on Day 90	Estimand 1 (see above)

 Version No:

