10.1.2. Secondary estimands

• For a given endpoint, the secondary estimand will be the population average treatment effect on the change from baseline at a given time assessment (i.e., on Day 16, Day 45 or Day 90) of nirmatrelvir/ritonavir compared to placebo/ritonavir. Measurements after discontinuation of study intervention will be censored and treated as missing data. Missing data due to censoring, study withdrawal or other reasons (e.g., laboratory failure) will have data imputed based on a missing at random (MAR) assumption. Participants with inadequate compliance will have their values used as-is in the analysis. The

 Version No:

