10.4. Statistical methods

For the primary estimand of the primary endpoint, a linear mixed model (LMM) with subject-specific random intercept will be specified to assess possibles changes over time within and among groups. LMM accounts for both fixed and random effects, can analyze data with repeated measures as well as can handle missing values. Specifically, the LMM will include treatment, time, and time*treatment interaction term as fixed effects, and subject/participant as a random effect. An unstructured correlation matrix will be used. Missing values will be imputed as part of the LMM model assumptions.

No adjustments will be made for multiplicity.

For continuous variables, differences in mean or median between groups will be assessed using Student's t-test (parametric) or Mann-Whitney test (non-parametric) depending on the

 Version No:

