10.5. Sample size calculations

The statistical power to detect a 10-unit placebo/ritonavir adjusted improvement from baseline to Day16 (primary endpoint) was estimated using the following assumptions: a 2:1 case-control ratio, nominal significance of alpha=0.05, 1-tailed test and 90 % power. Based on these assumptions, the study population would need to be at least 207 patients. In the study, ~400 participants will be randomized to a) have at least 207 completers to account for 48% dropouts during the execution of the study and b) increase the statistical power for the secondary endpoints of the study that will only be measured in the subset of patients with POTS, and for the secondary endpoints for which the variabilities in the Swedish post-covid patient population are not well documented.

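### Section 10.1 labels the effect over time as the primary estimand and the Day 16 effect as secondary, so the Day 16 test that was powered is not fixed as the primary test

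*Protocol*

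**What the plan says.** Most of the protocol points to one visit.

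- **Endpoint.** The synopsis (Section 1) and Section 4.2 give the primary endpoint as "Change from baseline on the EQ-5D-5L VAS scale at day 16". Days 45 and 90 on the same scale are secondary endpoints.
- **Hypothesis.** Section 10 states as H0 that "there is no placebo-adjusted difference in EQ-5D-5L between nirmatrelvir/ritonavir and placebo/ritonavir at Day 16". It then makes testing of a sustained difference at Days 45 and 90 conditional on a positive primary endpoint.
- **Sample size.** Section 10.5 is built to detect a "10-unit placebo/ritonavir adjusted improvement from baseline to Day16 (primary endpoint".

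The estimand sections read differently.

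- **Section 10.1.1**, written for any endpoint: "the primary estimand will be the population average treatment effect on the change from baseline over time of nirmatrelvir/ritonavir compared to placebo/ritonavir". No visit is named.
- **Section 10.1.2**, also for any endpoint: "the secondary estimand will be the population average treatment effect on the change from baseline at a given time assessment (i.e., on Day 16", with Days 45 and 90 listed after it.
- **Section 4.2**, Estimand 1, attached to the primary endpoint: the first sentence describes a mean effect "on a continuous endpoint over time for all randomized/evaluable participants"; the second gives "The difference of Day 16 on EQ-5D-5L VAS scale between the nirmatrelvir/ritonavir and placebo arms in participants with long COVID estimated with a longitudinal analysis".
- **Section 10.4**: "For the primary estimand of the primary endpoint, a linear mixed model (LMM) with subject-specific random intercept" is specified, with treatment, time and their interaction as fixed effects, in order to look at changes over time within and between groups. It does not say which contrast or test decides the trial.

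**The concern.** Read literally, Section 10.1 gives the secondary label to the only quantity that is hypothesised and powered, and the primary label to a quantity with no stated visit and no sample size behind it. Section 10.4 then ties the model to whatever the primary estimand is. EQ-5D-5L is collected at Days 16, 45 and 90, so the same fitted model can yield a Day 16 contrast, a contrast averaged over the three visits, or an interaction test. All three could be reported as the primary result.

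These answer different questions and can disagree. An averaged effect can be positive when there is no effect at Day 16, and it can miss a Day 16 effect of the size the trial was planned for. The choice also decides whether the conditional testing of Days 45 and 90 opens. If the contrast is chosen only after unblinding, any choice is open to the charge of selection.

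**Working it through.** **1. Sections side by side**

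| Place | Time of the effect | Label |
|---|---|---|
| Sections 1 and 4.2, endpoint | Day 16 | primary |
| Section 10, H0/H1 | Day 16 | primary |
| Section 10, conditional testing | Days 45 and 90, after a positive primary | additional |
| Section 10.5 | Day 16 | primary |
| Section 4.2, Estimand 1, first sentence | over time | primary |
| Section 4.2, Estimand 1, second sentence | Day 16 | primary |
| Section 10.1.1 | over time | primary |
| Section 10.1.2 | Day 16, 45 or 90 | secondary |
| Section 10.4 | over time, no contrast named | model for the primary estimand |

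The conflict lies between stated rules. It is not a gap left for later detail.

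**2. The protocol's own figure**

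Inputs from Section 10.5: difference 10, allocation 2:1, one-sided alpha 0.05, power 90%, N = 207 (138:69). No SD is stated, so 207 cannot be reproduced independently. Solving backwards:

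SD = 10 / [(1.645 + 1.282) × √(1/138 + 1/69)] = 10 / (2.927 × 0.1474) ≈ 23.2

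An SD of 23.1 gives 69 + 138 = 207 exactly after rounding up. For dropout, 207 / (1 − 0.48) = 398.1, or 399, which agrees with about 400 randomised. The calculation is a comparison of two means at Day 16 and nothing else.

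**3. What the choice of contrast does**

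Assumptions: 138:69, one-sided 5%, SD of change 23.2, equal at each visit, and the same correlation ρ between any two visits, with ρ = 0.3, 0.5 or 0.7. Normal approximation.

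- Standard error of the Day 16 contrast: 23.2 × 0.1474 ≈ 3.42.
- Standard error of the three-visit average: 3.42 × √((1 + 2ρ)/3) ≈ 2.50, 2.79 and 3.06 for ρ = 0.3, 0.5 and 0.7.
- Power = Φ(effect / standard error − 1.645).

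For example, with effects 10/5/0 the mean effect is 5. At ρ = 0.5, 5/2.79 − 1.645 ≈ 0.15, which gives 56%.

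| True effect at Days 16/45/90 | Day 16 contrast | Average, ρ = 0.3 | ρ = 0.5 | ρ = 0.7 |
|---|---|---|---|---|
| 10/10/10 | 90% | 99% | 97% | 95% |
| 10/5/5 | 90% | 85% | 77% | 70% |
| 10/5/0 | 90% | 64% | 56% | 50% |
| 10/0/0 | 90% | 38% | 33% | 29% |
| 0/0/10 | 5% | 38% | 33% | 29% |

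In the last row H0 at Day 16 is true. The mean effect is again 10/3, so the average has the same chance of a positive result as in the row above.

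The interaction test is left out of the table. Its power depends on whether baseline is one of the repeated measures, which Section 10.4 does not say.

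**The case against.** A reader might infer that the primary analysis simply is not the test that was powered. The documents do not support that. Section 10.1.1 is a generic definition, and the endpoint it is applied to is itself a Day 16 change. Section 4.2 assigns Estimand 1 to that endpoint and ends with the Day 16 difference from a longitudinal analysis. A mixed model with treatment, time and their interaction is such an analysis and can deliver that contrast. The conditional testing in Section 10 also counts against a three-visit average: such an average would draw on Day 45 and Day 90 data that the protocol treats as secondary and examines only after Day 16 succeeds. No section names an average or the interaction as the primary test.

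It can also be said that coding visit as categorical and naming the contrast are normally left to the SAP, which is not shown here. That is fair, and the absence of those details alone would not be a finding.

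All of this stands against the stronger claim. It does not remove the contradiction. Section 4.2 contains both readings in one cell and reuses Estimand 1 for the Day 45 and 90 VAS endpoint and for most other secondary endpoints. Section 10.1 gives the Day 16 effect the secondary label outright. An SAP that chooses Day 16 departs from Section 10.1.1; one that chooses the effect over time departs from H0 and Section 10.5. The SAP cannot follow both.

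**Conclusion.** The point holds as a contradiction in the protocol. The endpoint, H0/H1, the conditional testing, the sample size and one sentence of Estimand 1 set the primary question at Day 16. Sections 10.1.1 and 10.1.2 reverse the labels, and Section 10.4 names no deciding contrast. Day 16 is the most plausible intention, but the text does not fix it.

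The power figures illustrate what is at stake. They do not describe an analysis that the protocol specifies. They rest on a back-solved SD, equal SDs across visits, assumed correlations and assumed effect patterns. Within those assumptions, averaging over visits moves power for a 10-unit Day 16 effect from 90% to anywhere between 29% and 99%. It also gives a positive result 29–38% of the time in a pattern with no Day 16 effect (0/0/10).

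**What to change.** - **Section 10.1.1:** define the primary estimand for EQ-5D-5L VAS as the between-arm difference in mean change from baseline at Day 16.
- **Section 10.4:** name the single Day 16 treatment contrast from the mixed model, with visit as a categorical factor, as the primary test.
- **Section 10.1.2:** make the effect over time a secondary estimand.
- **Section 4.2:** align the first sentence of Estimand 1 with its second for the primary endpoint.

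The cost is wording in the protocol and matching text in the SAP, agreed before unblinding. The sponsor would need to judge under Section 13 whether the change counts as substantial. The sample size stays at 207 completers and about 400 randomised, and data collection does not change.
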